At visit 1, Subjects will undergo epicutaneous hypersensitivity skin testing to grass allergens prevalent in southern California: Johnson Grass (Sorghum Halepense), Bermuda Grass (Cynodon Dactylon), and Timothy Grass (Phleum Pretense), along with dog, cat and perennial allergens: dust mite (dermatophagoides pteronyssinus, dermatophagoides farina), and common mold allergens (alternaria, aspergillus, cladosporium, and penicillium) (36). Subjects with positive skin test results to one or more grass allergens and either negative skin test to perennial allergens (dust mite or mold) or positive tests to perennial allergens (dust mite or mold) without a correlating clinical history consistent with perennial allergic rhinitis will undergo grass allergen nasal provocation testing. Subjects with a positive skin test to cat or dog and clinical symptoms consistent with cat or dog triggered allergic rhinitis will be asked to avoid cats and or dogs for the entire study. For subjects who have an epicutaneous allergen skin or blood test on file completed by the VA Allergy Clinic within <1 year that confirms a positive to grass pollens the results will be used to proceed onto the up-dosing nasal challenge. Subjects experiencing a positive nasal provocation test defined by a total nasal symptom score (TNSS) over 7, or PNIF is reduced by  $\geq$  50% from baseline redaing will be tested for serum GSTM1 polymorphism and baseline sulforaphane levels and will proceed to visit 2. Subjects failing to mount a positive response with the highest concentration (10,000 BU/cc for p. phleum and c. cynodon, or 1:100 w/v for s. sorghum) will be withdrawn from the study...

Nasal challenge will repeat at visit 2, two weeks after visit 1, and visit 3, 3 weeks after beginning intervention at visit 2. This challenge was developed and perfected by Guy W. Scadding PhD and colleagues and showed reproducibility in a 2012 study (36). Prior to and following each challenge, subjects will undergo spirometry. Challenges will not be performed in patients with forced expiratory volume in 1 second (FEV1) values less than 70%. The visit 1 nasal challenge will be considered a graded up-dosing challenge needed to determine the dose used at visits 2 and 3.

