### Study Outcome Measures:

1. The Total Nasal Symptoms Score (TNSS), performed to determine adequate dosing for nasal challenge (visit 1) and during the nasal challenges (visit 2, 3). During the challenge the TNSS will be taken 30 minutes after nasal lavage, and then repeated at 5, 15, and 30 minutes then hourly to 4 hours post-challenge.

2. The peak nasal inspiratory flow (PNIF) performed at the up-dosing nasal challenge visit (visit 1) and during nasal challenges (visit 2 and 3). During the challenge, PNIF will be taken 30 minutes after the nasal lavage, then repeated at 5, 15 and 30 minutes after the challenge, then hourly to 4 hours post-challenge.

3. Biomarker measurements taken from nasal fluid collected by nasal sponge at visit 2 and visit 3 will include:

a) IL-4: 0 mintue, 5 minutes, 15 minutes, 30 minutes, then hourly to 4 hours post challenge
b) IL-5: 0 minute, 5 minutes, 15 minutes, 30 minutes, then hourly to 4 hours post challenge
c) IL-13: 0 minute, 5 minutes, 15 minutes, 30 minutes, then hourly to 4 hours post challenge
d) Eosinophil Cationic Protein (ECP): 0 minute, 5 minutes, 15 minutes, 30 minutes, then hourly to 4 hours post challenge

e) Tryptase: 0 minute, 5 minutes, 15 minutes, 30 minutes, then hourly to 4 hours post challenge

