#### Procedures performed

Skin Testing: Epicutaneous skin testing is considered highly reliable, safe and widely used in diagnosing allergic rhinitis (37). After application of the specific allergen to the sterile tip of the applicator, the subject's skin will be gently lifted and the tip containing allergen will be applied. Along with application of the allergens mentioned, histamine and a saline control will be applied to subject's skin. Results will be interpreted 20 minutes following and will be considered positive if the wheal and erythema are at least 3mm larger than the saline control. For subjects who have an epicutaneous allergen skin or blood test on file completed by the VA Allergy Clinic within  $\leq 1$  year that confirms a positive to grass pollens the results will be used to proceed onto the up-dosing nasal challenge.

Nasal Challenge: Nasal Challenge is considered a safe and useful diagnostic tool in diagnosing causes of both allergic and nonallergic rhinitis *(38)*. The nasal challenge chosen was based on repeated reliability using the TNSS and PNIF scores along with the biomarkers chosen for this study. (36)

Subjects will undergo an up-dosing nasal challenge performed at visit 1 in order to determine the threshold dose to be given at the subsequent nasal challenges (visit 2 and visit 3). During the up-dosing nasal challenge, the TNSS will be recorded immediately before each subsequent dose. Grass allergen extract (*c. cynodon, p. pretense or s. sorghum*,) will be used in the

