challenge. For c. cvnodon (Bermuda grass), dosing will start at 30 BU/ml and will continue with the following concentrations until a TNSS score reaches 7 or greater or PNIF is reduced by >50% from baseline reading: 300, 1000, 3000 and 10,000 BU/ml. For p. pretense(Timothy grass), dosing will start at 300 and will continue with the following concentrations until a TNSS score reaches 7 or greater or baseline PNIF is reduced by > 50% from baseline reading: 1,000,3,000,10,000 and 100,000 BU/ml. For s. sorghum (Johnson grass) dosing will start at 1:200,000 and will continue with the following concentrations until a TNSS score reaches 7 or greater or baseline PNIF is reduced by > 50% from baseline reading: 1:20,000, 1:2000, 1:200, and 1:20 w/v. Subjects will receive three sprays equivalent to 100 µl for each concentration into each nostril using an atomizer device, part of the standardized equipment at VAGLAHS for patients requiring nasal sprays during procedures applied every 10 minutes until maximal concentration or a TNSS score of 7 or PNIF reduction by  $\geq$  50% from baseline reading is achieved. Prior to subsequent challenges at visit 2 and 3, nasal lavage (SinusRinse) will be performed. A baseline PNIF and TNSS will be recorded 30 minutes following nasal layage for visits 2 and 3. Nasal challenge with 100 µl of the final dose achieved at visit 1 will then be applied into each nostril. The PNIF and TNSS will be recorded following challenge at 5, 15, 30 minutes following challenge and then at 1 hour, continuing to record each hour for 4 hours. During these intervals, nasal sponges (Plastocell & Co.) will be applied into each nostril onto the nasal mucosa, beyond the nasal vestibule, and alongside the inferior turbinate with the use of a crock forceps (Phoenix surgical instruments, Harlow, UK) and a Thuddicum's nasal speculum (Phoenix surgical instruments, Harlow, UK). After two minutes of placement, the sponges will be removed and then added to 2 ml centrifuge tubes with indwelling .22µm cellulose acetate filters (Costar Spin-X, Corning, NY, USA) and placed immediately into ice before centrifuging within the hour. The liberated fluid will then be freezed at -80° until analysis occurs.

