General physical examination: A physical examination to determine general health to include measurement of vitals and a cardiopulmonary examination will be performed in the VA GLA Allergy/Immunology Clinic by the attending physician. A *nasal examination* will be performed at every visit before any nasal challenge or lavage is performed. On Day 1, a urine pregnancy test will be performed for women of child-bearing potential.

The Immediate Total Nasal Symptom Score (TNSS): The TNSS has been used in prior interventional studies to evaluate different treatment modes for allergic rhinitis (*39, 40*, and 41). The score will consist of subjects rating 4 symptoms (nasal congestion/postnasal drainage, nasal pruritus, rhinorrhea, or sneezing) on a scale of 0 to 3, where 0=no symptoms present, 1=mild symptoms that do not interfere with activity, 2=moderate symptoms that are slightly bothersome symptoms with slight interference with activity and/or nighttime sleep, or 3=severe symptoms with interference with activity and nighttime sleep.

The Peak Nasal Inspiratory Flow (PNIF): the PNIF (Alliance Tech Medical) has been used in prior interventional studies involving allergic rhinitis (42, 43, and 44). Patients exhales fully and quickly after checking that an air tight seal covers the nose and seals the mouth.

Nasal Examination: Nasal examination will be performed at each visit prior to nasal challenge. Each nasal examination will include use of an otoscope with specula inserted into the nasal passage. Nasal passages and nasal turbinates will be inspected for color, swelling, exudate or bleeding.

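### The top TNSS level depends on nighttime sleep, which an in-clinic challenge cannot show, so severe symptoms in clinic have no defined score

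*Combined protocol and SAP*

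**What the plan says.** The scale is defined in the combined protocol and SAP, Procedures performed, in the entry for the Immediate Total Nasal Symptom Score. "The score will consist of subjects rating 4 symptoms", each from 0 to 3. Level 2 is labelled moderate and allows "slight interference with activity and/or nighttime sleep". Level 3 reads "3=severe symptoms with interference with activity and nighttime sleep". Level 2 joins activity and sleep with *and/or*; level 3 joins them with *and*.

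The score is rated at these times:

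- **Visit 1 up-dosing** (Procedures performed, Nasal Challenge): "the TNSS will be recorded immediately before each subsequent dose", with doses 10 minutes apart.
- **Visits 2 and 3** (Study Outcome Measures): once before challenge, "then repeated at 5, 15, and 30 minutes then hourly to 4 hours post-challenge". The Nasal Challenge text agrees: "continuing to record each hour for 4 hours".

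The score is used in three ways:

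- **Qualification.** Overview of Study Design requires a "total nasal symptom score (TNSS) over 7" or a PNIF fall of at least 50%.
- **Challenge step.** Nasal Challenge continues "until a TNSS score reaches 7 or greater" or until PNIF falls by about 50%. The step reached is carried to visits 2 and 3.
- **Primary endpoint.** The Statistical Considerations name TNSS as primary, averaged over late readings from 3 hours and analysed by ANCOVA adjusted for the visit 2 value.

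No section gives separate wording for in-clinic ratings.

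**The concern.** A participant can judge interference with activity while sitting in the clinic, but cannot judge interference with a night that has not yet come. Level 3 needs both, so its definition cannot be met within the rating window.

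This leaves a gap in the scale. Severe symptoms that clearly interfere with activity in the clinic are more than level 2, which is moderate with slight interference. They also fall short of level 3 as written. Each participant, or whoever hands over the score sheet, has to improvise. Some will stop at 2 because the sleep condition is not met. Others will choose 3 because the word *severe* fits.

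Two people with the same symptoms can then differ by up to one point per item. That difference enters the primary endpoint. At visit 1 it also enters the TNSS criterion, so a literal rater who has not met the PNIF criterion may go on to a further up-dosing step where another rater with the same symptoms would have stopped.

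**Working it through.** **1. Range of the score.** Inputs are 4 items, each 0 to 3, from the TNSS entry.

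- As labelled: 4 × 3 = 12.
- Read literally, with no item above 2: 4 × 2 = 8.

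**2. What the cut-offs demand under each reading.** All item patterns were counted (4⁴ = 256 on 0–3; 3⁴ = 81 on 0–2).

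| TNSS criterion | Items 0–3 | Items 0–2 (literal) |
|---|---|---|
| 7 or more (Nasal Challenge) | 106 of 256 | 5 of 81 |
| Above 7 (Overview of Study Design) | 66 of 256 | 1 of 81 |

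Under the literal reading, 7 or more needs at least three items at 2 and the fourth at 1 or 2. Above 7 needs 2 on all four. As a share of the range, 7/12 = 58% and 7/8 = 88%. The counts show how strict a cut-off is. They are not probabilities, and both cut-offs stay reachable.

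**3. The plan's own power figure.** Inputs from the sample size paragraph: difference 1.5, SD 2.08, alpha 0.025, 36 per arm, two-sample t-test, 80% power. Sidedness is not stated; two-sided fits best.

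- Normal approximation: n = 2(2.2414 + 0.8416)² × 2.08² / 1.5² = 36.6, so 37 per arm. At 36 per arm, 1.5 / (2.08 × √(2/36)) − 2.2414 = 0.818, which gives power 0.793.
- Exact t-test: power 0.777 at 36 per arm and 0.802 at 38 per arm (152/4).

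The stated figure is reproduced approximately.

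**4. What a universal cap at 2 would do to power.** The documents give no expected TNSS at 3 to 4 hours, so this is an illustration over a range of control means. Assumptions:

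- Each item is a latent normal value, rounded and clipped to 0–3 or 0–2, with latent inter-item correlation 0.4.
- The control SD is 2.08 and the true difference is 1.5, both on the 0–12 scale.
- There are 36 per arm, with a two-sided t-test at 0.025.
- Every participant reads the anchors literally.

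| Control mean (0–12) | Power, 0–12 | Difference, 0–8 | Pooled SD, 0–8 | Power, 0–8 |
|---|---|---|---|---|
| 3 | 0.870 | 1.46 | 1.79 | 0.875 |
| 4 | 0.824 | 1.44 | 1.89 | 0.825 |
| 5 | 0.801 | 1.39 | 1.89 | 0.797 |
| 6 | 0.786 | 1.30 | 1.82 | 0.770 |
| 7 | 0.775 | 1.14 | 1.67 | 0.728 |
| 8 | 0.758 | 0.94 | 1.48 | 0.657 |

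The cap shrinks the difference and the SD together. At mean 5 the standardised difference hardly moves: 1.50/2.02 = 0.743 becomes 1.39/1.89 = 0.735. At mean 8 it falls from 1.50/2.13 = 0.704 to 0.94/1.48 = 0.635.

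The illustration leaves out baseline adjustment and the averaging of late readings. It also does not model a mix of literal and lenient raters, so the noise from inconsistent use is not sized here.

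**The case against.** The strongest reply is that this is a matter of wording with limited consequences. Much of it stands.

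- **Labels.** The levels also carry the words mild, moderate and severe, under a title that says the score is immediate. Many participants may simply rate by label. A reader might infer from the anchor that the maximum is 8 in this trial. The documents do not support that: 8 follows only if everyone reads the anchor literally. The reply does not repair the definition, though, because it relies on participants setting aside a stated condition.
- **PNIF.** A reader might infer that TNSS alone decides who is randomised and at which challenge step. It does not. Both the qualification rule and the up-dosing rule can be met by a PNIF fall of about 50%. This softens the entry problem and has no bearing on the primary endpoint.
- **Late endpoint.** A reader might infer that the primary endpoint is compressed and the trial underpowered. That is not shown. The endpoint is a late average, not the peak response, and its expected level is not given. The table shows almost no loss at control means of 3 to 5.
- **Design protections.** Treatment is randomised and assessment is blinded, so individual rating habits should not systematically favour an arm. ANCOVA on the visit 2 value absorbs part of a stable habit. It cannot correct a habit that changes between visits 2 and 3, nor a challenge step already fixed at visit 1.

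**Conclusion.** The point holds in a limited form. It is certain that the level 3 anchor does not fit the period over which the score is rated, and that no in-clinic definition is given. Severe symptoms in clinic therefore have no defined score on the primary endpoint or on the TNSS route to qualification and challenge step.

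The size is uncertain. Inconsistent scoring between people is at least as plausible a result as a uniform ceiling, and it would act mainly as noise. If everyone did stop at 2, the maximum would be 8, and the effect on power would depend on late scores. Under the assumptions above, power changes by less than 1 percentage point at control means of 3 to 5. It falls by about 5 points at mean 7 (0.78 to 0.73) and about 10 at mean 8 (0.76 to 0.66). These figures take the analysis window as 3 and 4 hours. The endpoint sentence is incomplete at that point, and the sample size paragraph names hours beyond the last reading.

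The wording should be corrected, because it is a stated scoring rule for the primary endpoint and the change is cheap.

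**What to change.** In the TNSS entry under Procedures performed, state that at every challenge assessment the participant rates each symptom as it is right now. Use in-clinic anchors (0 none, 1 mild, 2 moderate, 3 severe), remove the nighttime-sleep clauses from levels 2 and 3, and use identical wording at visits 1, 2 and 3.

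If enrolment has begun, keep each participant on one version throughout and record which version was used.

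The cost is a short text change and a matching score sheet, with no added visits, participants or measurements. The downside is that the anchors may no longer match a source that used the sleep wording, so comparison with its scores would need care.

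Separately, the TNSS criterion in Overview of Study Design (above 7) and the one in Nasal Challenge (7 or more) differ and must be reconciled.

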# Precautions:

Since allergen will be administered through nasal challenge, it is imperative that the study take place in a controlled environment that is prepared to treat hypersensitivity reactions. The VAGLAHS Allergy/Immunology clinic has the appropriate equipment and trained personnel to treat allergic reactions including anaphylaxis. A crash cart is available inside the clinic and epinephrine is readily available. The clinic is located within the VAGLAHS hospital where there are physicians trained in advanced cardiac life support (ACLS).

# Visit Target Windows:

Subject visit times during the treatment phase of the protocol should be consistent, within -+10 days of targeted scheduled visit days.

### **Randomization:**

This is a double blind randomized study. The subject randomization will be carried out based on a computer generated randomization list with a random blocked design of block sizes of 4 and 8. Only the study statistician and pharmacist will maintain the randomization list, the treatment administrators and outcome evaluators are blind to the randomization. The investigator performing and recording the results of the challenge will be blinded to the subjects assigned treatment arm.

# PAYMENT OFFERED FOR PARTICIPATION

Twenty dollars (\$20.00) will be paid to participants who complete up to the skin test procedure at visit 1, and do not meet study qualifications (skin test results determine that you not allergic to grass) to continue participation in the study.

Forty-five dollars (\$45.00) will be paid to participants who meet study qualifications and complete visit 1.

Ninety dollars (\$90.00) will be paid to participants who complete visit 2.

Ninety dollars (\$90.00) will be paid to participants who complete visit 3.

Additionally, those participants who will comply with study protocol and complete all three study visits will receive the completion of study payment in amount of \$75 at the end of the study.

# Study Material and analysis:

Choosing cytokines mediators:

TH2 cytokines (IL4, IL15, IL13): These cytokines direct production of IgE antibodies which latter attach to mast cells.

Tryptase, Eosinophilic Cationic Protein (ECP): Tryptase is immediately released from mast cells upon activation. ECP marks presence of eosinophils which are involved in the delayed reaction of allergic rhinitis.

Both the above cytokines, tryptase and ecp have been found in nasal mucus and levels have been replicated in prior nasal challenge (36)

#### Analysis of biomarkers:

All the following analysis will be performed at the biomarker lab, UCLA Center for Human Nutrition. Measurements of IL-4, IL-5, and IL-13 will be performed using MSD Human TH1/TH2 7-Plex, Ultra-Sensitive Kit according to the manufacturer's instructions (MS6000 7 spot, Meso Scale Discovery, Maryland, USA). Plates will read using anMSD SECTOR® 6000 instrument. With this method, validation procedures demonstrated that the lower quantification limit for all cytokines was approximately 5 pg/ml, with an assay range of 5–5000 pg/ml in nasal secretions.

All measurements will be performed on undiluted nasal fluid samples in duplicate and reported as mean values, though cytokine levels will be standardized with ng/ml protein concentration. Tryptase and Eosinophilic Cationic Protein (ECP) will be measured through ImmunoCAP at the minimum level of detection of 2mg/ml. Each plate/Immunocap carousel is run with standards and curve controls.

# Genomic DNA Isolation:

Peripheral blood will be drawn into a BD Vacutainer K2 EDTA tube (BD Biosciences; San Jose, CA). Genomic DNA will be extracted from blood using the GenElute Mammalian Genomic DNA Miniprep Kit (Sigma-Aldrich; St. Louis, MO) according to manufacturer's instructions. Briefly, 200 µl blood will be treated with Proteinase K followed by RNase for 2 min before lysing cells in a 55 deg C water for 10 min. DNA will be precipitated with 100% ethanol and bound to a spin column. After two washes, DNA will be eluted from column with TE buffer. TaqMan Polymerase Chain Reaction Genotyping of GSTP1 Ile105Val Genotyping will be performed using SNP Genotyping Assays for GSTP1 (rs1695) (Applied Biosystems; Foster City, CA) on a StepOnePlus Real-Time PCR Machine (Applied Biosystems). Real-time PCR will be performed with 25 ng DNA in a 20 µl reaction containing TaqMan Genotyping Master Mix and SNP genotyping assay. Reactions will be heated for 95 oC for 10 minutes following by 40 cycles of 92 oC for 15 sec with 60 oC for 1 min. Alleles will be determined using the allelic discrimination plot in the StepOne software genotyping program. Each sample will be performed in quadruplicate.

GSTM1 Copy Number-GSTM1 copy number will be determined using Pre-designed TaqMan Copy Number Assays (Applied Biosystems). GSTM1 will run in a duplex assay with RNase P as a reference gene. Reactions will be heated for 95 oC for 10 minutes following by 40 cycles of 92 oC for 15 sec with 60 oC for 1 min. Results will be analyzed using Copy Caller version 1.0 software (Applied Biosytems). Each sample is performed in quadruplicate.

# Measurement of sulforaphane:

HPLC-MS/MS identification of SFN metabolites in plasma R, S-sulforaphane will be purchased from LKT Laboratories, Inc. (Minnesota, USA). All solvents and other chemical used will be HPLC grade and were purchased from Fisher Scientific (USA). Water will be ultrafiltered using a Milli-Q pure water system. To the 4° C plasma sample (200  $\mu$ L) in a 1.5mL micro centrifuge tube (Fisher Scientific, USA), pre-cooled (4° C) trifluoroacetic acid (20  $\mu$ L) (TFA) will be added to precipitate plasma proteins (30 seconds) in the sample followed by brief mixing and refrigerated centrifugation at 15900×g for 10 min. The resulting supernatant will be filtered (0.2  $\mu$ m pore size) and 20  $\mu$ L injected for analysis.

A LCQ Advance mass (Thermo Finnegan) and a Survey HPLC equipped with binary pump, degasser, cooled auto-sampler and a PDA detector (USA) were used for the LC–MS analysis. The HPLC column will be a Zorbax SB- will be 0.25 mL/min and gradient elution will be used: solution A (1% acetic acid solution): solution B (acetonitrile). The gradient started at 2% solution B increasing over 20 min to 30% B and 50% in 30 minutes, finally re-equilibrating to 2% B for 10 min. The mobile phase solutions were filtered through 0.22 µm pore size cellulose nitrate or nylon membrane filters using a vacuum filtration apparatus. The LC eluent flow of 0.25 mL/min will be sprayed into the mass spectrometer interface without splitting. Electrospray ionization in the positive mode (ESI+) will be applied. The analytes are identified by molecular weight and their MS/MS, respectively. The identification of the MS/MS of SFN-Cys, SFN-Cys-Gly; SFN-NAC; and SFN-GSH at m/z of 178; 179; 178 and 179, respectively were used to confirm consumption of the BSE supplement by subjects in the study.

